**Table 14.1.3**  
**Demographic and Screening Characteristics (continued)**  
**Intent-To-Treat (ITT) Population**

	IM		IM		Total (N=XX)
	HIV Infected (N=XX)	HIV Uninfected (N=XX)			
Temperature (C)	N Mean (SD) Median 25%-75% Min-Max	XX XX.XX (XX.XXX) XX.XX XX.X - XX.X XX.X - XX.X	XX XX.XX (XX.XXX) XX.XX XX.X - XX.X XX.X - XX.X	XX XX.XX (XX.XXX) XX.XX XX.X - XX.X XX.X - XX.X	XX
Heart Rate (beats/min)	N Mean (SD) Median 25%-75% Min-Max	XX XX.X (XX.XX) XX.X XX - XX XX - XX	XX XX.X (XX.XX) XX.X XX - XX XX - XX	XX XX.X (XX.XX) XX.X XX - XX XX - XX	XX
Respiration Rate (breaths/min)	N Mean (SD) Median 25%-75% Min-Max	XX XX.X (XX.XX) XX.X XX - XX XX - XX	XX XX.X (XX.XX) XX.X XX - XX XX - XX	XX XX.X (XX.XX) XX.X XX - XX XX - XX	XX
Systolic Blood Pressure (mmHg)	N Mean (SD) Median 25%-75% Min-Max	XX XX.X (XX.XX) XX.X XX - XX XX - XX	XX XX.X (XX.XX) XX.X XX - XX XX - XX	XX XX.X (XX.XX) XX.X XX - XX XX - XX	XX
Diastolic Blood Pressure (mmHg)	N Mean (SD) Median 25%-75% Min-Max	XX XX.X (XX.XX) XX.X XX - XX XX - XX	XX XX.X (XX.XX) XX.X XX - XX XX - XX	XX XX.X (XX.XX) XX.X XX - XX XX - XX	XX

N = All subjects enrolled, and denominator for percentage calculations.

[1] One or more race(s) may be recorded, therefore, a patient may be counted in more than one category and percentages may add up to more than 100%.

NOTE: The table shows data at Screening visit. If vital signs are missing at the Screening visit, the measurement at the Day 1 visit is used.

**Table 14.1.4**  
**Summary of Concomitant Medications**  
**Intent-To-Treat Population**

Medication Preferred Term	IM HIV Infected (N=XX) n (%)	IM HIV Uninfected (N=XX) n (%)	Total (N=XX) n (%)
XXXXXXXXXXXXXXXXXXXX	n (XXX.X%)	n (XXX.X%)	n (XXX.X%)
XXXXXXXXXXXXXXXXXXXX	n (XXX.X%)	n (XXX.X%)	n (XXX.X%)
XXXXXXXXXXXXXXXXXXXX	n (XXX.X%)	n (XXX.X%)	n (XXX.X%)
XXXXXXXXXXXXXXXXXXXX	n (XXX.X%)	n (XXX.X%)	n (XXX.X%)
XXXXXXXXXXXXXXXXXXXX	n (XXX.X%)	n (XXX.X%)	n (XXX.X%)
XXXXXXXXXXXXXXXXXXXX	n (XXX.X%)	n (XXX.X%)	n (XXX.X%)
XXXXXXXXXXXXXXXXXXXX	n (XXX.X%)	n (XXX.X%)	n (XXX.X%)
XXXXXXXXXXXXXXXXXXXX	n (XXX.X%)	n (XXX.X%)	n (XXX.X%)
XXXXXXXXXXXXXXXXXXXX	n (XXX.X%)	n (XXX.X%)	n (XXX.X%)
XXXXXXXXXXXXXXXXXXXX	n (XXX.X%)	n (XXX.X%)	n (XXX.X%)

---

N = All subjects enrolled.

*Note to Programmer: Include only CMCAT = 'GENERAL MEDICATIONS' and use CMDECOD for "Medication Preferred Term". Medications are not*

**Table 14.1.5**  
**Summary of Protocol Violations and Deviations**  
**Intent-To-Treat Population**

	IM HIV Infected (N=XX) n (%)	IM HIV Uninfected (N=XX) n (%)	Total (N=XX) n (%)
Protocol Violations	n (XXX.X%)	n (XXX.X%)	n (XXX.X%)
XXXXXXXXXXXXXXXXXXXX	n (XXX.X%)	n (XXX.X%)	n (XXX.X%)
XXXXXXXXXXXXXXXXXXXX	n (XXX.X%)	n (XXX.X%)	n (XXX.X%)
XXXXXXXXXXXXXXXXXXXX	n (XXX.X%)	n (XXX.X%)	n (XXX.X%)
	n XXX.X%)	n XXX.X%)	n XXX.X%)
Protocol Deviations	n (XXX.X%)	n (XXX.X%)	n (XXX.X%)
XXXXXXXXXXXXXXXXXXXX	n (XXX.X%)	n (XXX.X%)	n (XXX.X%)
XXXXXXXXXXXXXXXXXXXX	n (XXX.X%)	n (XXX.X%)	n (XXX.X%)
XXXXXXXXXXXXXXXXXXXX	n (XXX.X%)	n (XXX.X%)	n (XXX.X%)

---

N = All subjects enrolled.

*Note to Programmer: Use DVCAT to differentiate violations from deviations, and use DVDECOD for the first column of the table.*

Westat (Created on DDMYYYY)  
S:\TMB302\DA\_IM\SAS\t\_protviols

**Table 14.2.1**  
**Comparison of Geometric Mean Trough Concentrations for IM Injection to 15 Minute IV Infusions**  
**Intent-to-Treat Population**

Analysis Type	Results
Proportion of Subjects with Geometric Mean	
Ctrough $\geq$ 300 ng/ml (%)	n/NT (%)
15 Minute IV Infusion	n/NT (%)
IM Injection	xxxx
Relative Risk	(xxxx, xxxx)
90% Confidence Limits	xxxx
TOST P-values [1]	xxxx
Lower Margin	xxxx
Overall	xxxx
Upper Margin	xxxx
Fisher's exact test 2-tailed P-Value [2]	xxxx

[1] Two one-sided tests of significance (TOST) using Farrington-Manning Method and z-statistics, within an 80%-125% criteria.  
H0: P1 / P2  $\leq$  Lower Margin or  $\geq$  Upper Margin of the equivalence limits  
[2] Fishers Exact test H0: P1 is not different from P2

*Note to Programmer: SAS code provided in SAP. Any subject with at least some non-missing PK data is included*

Westat (Created on DDMMYYYY)  
S:\TMB302\DA\_IM\SAS\t\_trough1

**Table 14.2.2**  
**Comparison of Arithmetic Mean Trough Concentrations for IM Injection to 15 Minute IV Infusions**  
**Intent-to-Treat Population**

Analysis Type	Results
Proportion of Subjects with Arithmetic Mean C trough >= 300 ng/ml (%)	n/NT (%)
15 Minute IV Infusion	n/NT (%)
IM Injection	xxxx
Relative Risk	(xxxx, xxxx)
90% Confidence Limits	xxxx
TOST P-values [1]	xxxx
Lower Margin	xxxx
Overall	xxxx
Upper Margin	xxxx
Fisher's exact test 2-tailed P-Value [2]	xxxx

[1] Two one-sided tests of significance (TOST) using Farrington-Manning Method and z-statistics, within an 80%-125% criteria.  
H0: P1 / P2 <= Lower Margin or >= Upper Margin of the equivalence limits  
2] Fishers Exact test H0: P1 is not different from P2

*Note to Programmer: SAS code provided in SAP. Any subject with at least some non-missing PK data is included*

**Table 14.2.3**  
**90% Confidence Interval of the LOG Transform of the Ratio of the**  
**Geometric Means of AUC for IM Injection to 15 Minute IV Infusion**  
**Intent-to-Treat Population**

Analysis Type	Results
Type 3 Tests of Fixed Effects	
PK Period[2]	
F Value(df)	xxxx
Pr > F	xxxx
Administration Route(IVI or IM)	
F Value(df)	xxxx
Pr > F	xxxx
Group (HIV+ or HIV-)	
F Value	xxxx
Pr > F	xxxx
Estimates (IM/IVI)	
Estimate (Standard Error)	xxxx (xxxx)
t Value (df)	xxxx (xx)
Pf >  t	xxxx
90% Confidence Interval	(xxxxx, xxxx)
Back Transformed Estimates	
Mean Geometric Ratio	xxxx
90% Confidence Interval [3]	(xxxxx, xxxx)

[1] A pharmacokinetic bridge between the IM injection and IV infusion is demonstrated for AUC if the 90% confidence interval of log transform of the ratio of the geometric means for IM Injection (test product) to IV infusion (reference product) for the enrolled subjects in the study is within an 80%-125% criteria.

[2] To provide more substantial data, PK parameters were calculated twice for each subject, described as PK Period in the statistical analysis plan. [3] A pharmacokinetic bridge between the IM injection and IV infusion is demonstrated for AUC if the 90% confidence interval of log transform of the ratio of the geometric means for IM Injection (test product) to IV infusion (reference product) for the enrolled subjects in the study is within an 80%-125% criteria.

*Note to Programmer: SAS code provided in SAP. Any subject with at least some non-missing PK data is included.*

**Table 14.2.4.1**  
**Viral Load (copies/mL) and Changes from Baseline**  
**Intent-to-Treat Population - IM HIV Infected**  
**Total and by Period**

		IM HIV Infected (N=XX)		
		Initial Period 15 min IV Infusion	Investigational Period IM Injection	Follow-up Period 15 min IV Infusion
Baseline [1]	N	XX		
	Mean (SD)	XX.X (XX.XX)		
	Median	XX.X		
	25%-75%	XX - XX		
	Min-Max	XX - XX		
Day 15	N	XX		
	Mean (SD)	XX.X (XX.XX)		
	Median	XX.X		
	25%-75%	XX - XX		
	Min-Max	XX - XX		
Change from Baseline	N	XX		
	Mean (SD)	XX.X (XX.XX)		
	Median	XX.X		
	25%-75%	XX - XX		
	Min-Max	XX - XX		
Day 29	N	XX		
	Mean (SD)	XX.X (XX.XX)		
	Median	XX.X		
	25%-75%	XX - XX		
	Min-Max	XX - XX		
...				
End of Study				
...				
Change from Baseline				

N = All subjects in the ITT Population, and denominator for percentage calculations.

[figure not shown]
[1] Baseline is the last analyte value recorded on Day 1, prior to the first dose administration.

**Viral Load (log10 copies/mL) and Changes from Baseline  
Intent-to-Treat Population - IM HIV Uninfected  
Total and by Period**

	IM HIV Uninfected (N=XX)		
	Initial Period	Investigational 15 min IV Infusion	Follow-up Period IM Injection
	IV Infusion		
Baseline [1]			
	N	XX	
	Mean (SD)	XX.X (XX.XX)	
	Median	XX.X	
	25%-75%	XX - XX	
	Min-Max	XX - XX	
Day 15			
	N	XX	
	Mean (SD)	XX.X (XX.XX)	
	Median	XX.X	
	25%-75%	XX - XX	
	Min-Max	XX - XX	
Change from Baseline			
	N	XX	
	Mean (SD)	XX.X (XX.XX)	
	Median	XX.X	
	25%-75%	XX - XX	
	Min-Max	XX - XX	
Day 29			
	N	XX	
	Mean (SD)	XX.X (XX.XX)	
	Median	XX.X	
	25%-75%	XX - XX	
	Min-Max	XX - XX	
...			
End of Study			
...			
Change from Baseline			

N = All subjects in the ITT Population (displayed according to actual treatment received), and denominator for percentage calculations.

[1] Baseline is the last analyte value recorded on Day 1, prior to the first dose administration.

[figure not shown]

[1] Baseline is the last analyte value recorded on Day 1, prior to the first dose administration. When Screening is the only value, it becomes Baseline and is counted in the Baseline row and not in the Screening row.

[2] End of Study is Day 85 for subjects in the IM HIV Infected Group.

Note to programmer: This is an example from a previous study. Only actual scheduled visits should be displayed.

Westat (Created on DDMMYYYY)  
S:\TMB302\DA\_IM\SAS\g\_vllogmean

**Table 14.3.1.1.1**  
**Treatment-Emergent Adverse Events Summary**  
**Safety Population**

	IM HIV Infected (N=XX)	IM HIV Uninfected (N=XX)	Total (N=XX)
TEAE [1]	n (xxx.x%)	n (xxx.x%)	n (xxx.x%)
Serious TEAE [2]	n (xxx.x%)	n (xxx.x%)	n (xxx.x%)
TEAE with Death Outcome	n (xxx.x%)	n (xxx.x%)	n (xxx.x%)
TEAE Leading to Discontinuation	n (xxx.x%)	n (xxx.x%)	n (xxx.x%)
Suspected Adverse Reaction[3]	n (xxx.x%)	n (xxx.x%)	n (xxx.x%)
Severe TEAE [4]	n (xxx.x%)	n (xxx.x%)	n (xxx.x%)
Class C TEAE [5]	n (xxx.x%)	n (xxx.x%)	n (xxx.x%)

N = All subjects in the Safety Population (displayed according to actual treatment received), and denominator for percentage calculations.

TEAE = Treatment-Emergent Adverse Event.

NOTE: Identical TEAEs are counted only once per subject.

[1] Number(%) of subjects with at least one TEAE.

[2] Number(%) of subjects with at least one serious TEAE, excluding death, as identified by the investigator.

[3] Possibly related to study drug.

[4] Severity/Grade 3 or higher (severe or potentially life threatening).

[5] Per the CDC Classification System for HIV Infection.

**Table 14.3.1.2.1**  
**Overall Incidence of Treatment-Emergent Adverse Events**  
**Safety Population**

Body System	Preferred Term [1]	IM HIV Infected (N=XX)	IM HIV Uninfected (N=XX)	Total (N=XX)
Overall[2]	ALL TERMS Events	n (xxx.x%) n	n (xxx.x%) n	n (xxx.x%) n
	XXXXX Events	n (xxx.x%) n	n (xxx.x%) n	n (xxx.x%) n
	XXXXX Events	n (xxx.x%) n	n (xxx.x%) n	n (xxx.x%) n
	XXXXX Events	n (xxx.x%) n	n (xxx.x%) n	n (xxx.x%) n
XXXXXXX	ALL TERMS Events	n (xxx.x%) n	n (xxx.x%) n	n (xxx.x%) n
	XXXXX Events	n (xxx.x%) n	n (xxx.x%) n	n (xxx.x%) n

N = All subjects in the Safety Population (displayed according to actual treatment received), and denominator for percentage calculations.

NOTE: Identical TEAEs are counted only once per subject.

[1] "ALL TERMS" represents number(%) of subjects with at least one TEAE within that Body System;  
 "Events" represents number of TEAEs reported by the subject(s).

[2] Number(%) of subjects with at least one TEAE in any Body System.

**Table 14.3.1.3.1**  
**Incidence of Treatment-Emergent Adverse Events by Severity/Grade**  
**Safety Population**

		IM HIV Infected (N=XX)						
Body System	Preferred Term[1]	Any Grade [2]	Mild (Grade 1)	Moderate (Grade 2)	Severe (Grade 3)	Pot. Life Threatening (Grade 4)	Death (Grade 5)	
Overall [3]	ALL TERMS Events	n (XXX.X%) n	n (XXX.X%) n	n (XXX.X%) n	n (XXX.X%) n	n (XXX.X%) n	n (XXX.X%) n	
XXXXXXX	ALL TERMS Events	n (XXX.X%) n	n (XXX.X%) n	n (XXX.X%) n	n (XXX.X%) n	n (XXX.X%) n	n (XXX.X%) n	
XXXXXX	XXXX Events	n (XXX.X%) n	n (XXX.X%) n	n (XXX.X%) n	n (XXX.X%) n	n (XXX.X%) n	n (XXX.X%) n	
XXXXXX	XXXX Events	n (XXX.X%) n	n (XXX.X%) n	n (XXX.X%) n	n (XXX.X%) n	n (XXX.X%) n	n (XXX.X%) n	
XXXXXXX	ALL TERMS Events	n (XXX.X%) n	n (XXX.X%) n	n (XXX.X%) n	n (XXX.X%) n	n (XXX.X%) n	n (XXX.X%) n	
XXXXXX	XXXX Events	n (XXX.X%) n	n (XXX.X%) n	n (XXX.X%) n	n (XXX.X%) n	n (XXX.X%) n	n (XXX.X%) n	
XXXXXX	XXXX Events	n (XXX.X%) n	n (XXX.X%) n	n (XXX.X%) n	n (XXX.X%) n	n (XXX.X%) n	n (XXX.X%) n	
XXXXXXX	ALL TERMS Events	n (XXX.X%) n	n (XXX.X%) n	n (XXX.X%) n	n (XXX.X%) n	n (XXX.X%) n	n (XXX.X%) n	
XXXXXX	XXXX Events	n (XXX.X%) n	n (XXX.X%) n	n (XXX.X%) n	n (XXX.X%) n	n (XXX.X%) n	n (XXX.X%) n	
XXXXXX	XXXX Events	n (XXX.X%) n	n (XXX.X%) n	n (XXX.X%) n	n (XXX.X%) n	n (XXX.X%) n	n (XXX.X%) n	

N = All subjects in the Safety Population (displayed according to actual treatment received), and denominator for percentage calculations.

The table shows TEAEs (per subject) with the most severe occurrence, regardless of relationship to study drug.

[1] "ALL TERMS" represents number(%) of subjects with at least one TEAE within that Body System;

"Events" represents number of TEAEs reported by the subject(s).

[2] Adverse Events with missing severity grade are included in this column only.

[3] Number(%) of subjects with at least one TEAE in any Body System.

**Note to programmer:** Repeat this table for the IM HIV Uninfected Group and Total, all under the same table number.

**Table 14.3.1.4.1**  
**Incidence of Treatment-Emergent Adverse Events by Relationship to Study Drug**  
**Safety Population**

Body System	Preferred Term[1]	IM HIV Infected (N=XX)		IM HIV Uninfected (N=XX)		Total (N=XX)	
		Suspected Adverse Reaction [3]	Unrelated	Suspected Adverse Reaction [3]	Unrelated	Suspected Adverse Reaction [3]	Unrelated
		n (XXX.X%)	n (XXX.X%)	n (XXX.X%)	n (XXX.X%)	n (XXX.X%)	n (XXX.X%)
Overall[2]	ALL TERMS Events	n (XXX.X%) n	n (XXX.X%) n	n (XXX.X%) n	n (XXX.X%) n	n (XXX.X%) n	n (XXX.X%) n
XXXXXXX	ALL TERMS Events	n (XXX.X%) n	n (XXX.X%) n	n (XXX.X%) n	n (XXX.X%) n	n (XXX.X%) n	n (XXX.X%) n
XXXXX	Events	n (XXX.X%) n	n (XXX.X%) n	n (XXX.X%) n	n (XXX.X%) n	n (XXX.X%) n	n (XXX.X%) n
XXXXX	Events	n (XXX.X%) n	n (XXX.X%) n	n (XXX.X%) n	n (XXX.X%) n	n (XXX.X%) n	n (XXX.X%) n
XXXXXXX	ALL TERMS Events	n (XXX.X%) n	n (XXX.X%) n	n (XXX.X%) n	n (XXX.X%) n	n (XXX.X%) n	n (XXX.X%) n
XXXXX	Events	n (XXX.X%) n	n (XXX.X%) n	n (XXX.X%) n	n (XXX.X%) n	n (XXX.X%) n	n (XXX.X%) n
XXXXX	Events	n (XXX.X%) n	n (XXX.X%) n	n (XXX.X%) n	n (XXX.X%) n	n (XXX.X%) n	n (XXX.X%) n
XXXXXXX	ALL TERMS Events	n (XXX.X%) n	n (XXX.X%) n	n (XXX.X%) n	n (XXX.X%) n	n (XXX.X%) n	n (XXX.X%) n
XXXXX	Events	n (XXX.X%) n	n (XXX.X%) n	n (XXX.X%) n	n (XXX.X%) n	n (XXX.X%) n	n (XXX.X%) n
XXXXX	Events	n (XXX.X%) n	n (XXX.X%) n	n (XXX.X%) n	n (XXX.X%) n	n (XXX.X%) n	n (XXX.X%) n

N = All subjects in the Safety Population (displayed according to actual treatment received), and denominator for percentage calculations.

The table shows TEAEs (per subject) with the highest relationship, regardless of severity/grade.

[1] "ALL TERMS" represents number(%) of subjects with at least one TEAE within that Body System;

"Events" represents number of TEAEs reported by the subject(s).

[2] Number(%) of subjects with at least one TEAE in any Body System.

[3] Possibly related to study drug.

**Table 14.3.1.5.1**  
**Overall Incidence of Serious Adverse Events**  
**Safety Population**

*Note to programmer: Repeat above for SERIOUS Adverse Events with the footnote updated as below.*

N = All subjects in the Safety Population (displayed according to actual treatment received), and denominator for percentage calculations.

NOTE: Identical SAEs are counted only once per subject.

[1] "ALL TERMS" represents number(%) of subjects with at least one TEAE within that Body System;  
"Events" represents number of SAEs reported by the subject(s).

[2] Number(%) of subjects with at least one SAE in any Body System.

Westat (Created on DDMMYYYY)  
S:\TMB302\ DA\_IM \SAS\t\_aesae1

**Table 14.3.1.6.1  
Incidence of Serious Adverse Events by Relationship to Study Drug  
Safety Population**

*Note to programmer: Repeat tables above for SERIOUS Adverse Events with the footnote updated as below.*

N = All subjects in the Safety Population (displayed according to actual treatment received), and denominator for percentage calculations.

NOTE: The table shows related SAEs (per subject) with the highest relationship, regardless of severity/grade.

[1] "ALL TERMS" represents number(%) of subjects with at least one SAE within that Body System;

"Events" represents number of SAEs reported by the subject(s)

[2] Number(%) of subjects with at least one SAE in any Body System.

Westat (Created on DDMMYYYY)  
S:\TMB302\ DA\_IM \SAS\t\_aesaerell

**Table 14.3.1.7.1**  
**Treatment-Emergent Adverse Events Leading to Study Discontinuation**  
**Safety Population**

*Note to programmer: Repeat tables above for Adverse Events LEADING TO STUDY DISCONTINUATION (same footnote).*

Westat (Created on DDMMYYYY)  
S:\TMB302\ DA\_IM \SAS\t\_aedisc1

**Table 14.3.2.1**  
**Abnormal Laboratory Results by DAIDS Toxicity Grade [1] and Route of Administration**  
**Safety Population - IM HIV Infected Group**

Test/Route of Administration [2]	IM HIV Infected (N=XX)				
	Grade 0 n (%)	Grade 1 n (%)	Grade 2 n (%)	Grade 3 n (%)	Grade 4 n (%)
Analyte 1					
IV Infusion (Day 1 - Day 29)	n (xx.x%)	n (xx.x%)	n (xx.x%)	n (xx.x%)	n (xx.x%)
IM Injection (Day 30 - Day 85)	n (xx.x%)	n (xx.x%)	n (xx.x%)	n (xx.x%)	n (xx.x%)
Follow-up (Day 86 - Day 99)	n (xx.x%)	n (xx.x%)	n (xx.x%)	n (xx.x%)	n (xx.x%)
Analyte 2					
IV Infusion (Day 1 - Day 29)	n (xx.x%)	n (xx.x%)	n (xx.x%)	n (xx.x%)	n (xx.x%)
IM Injection (Day 30 - Day 85)	n (xx.x%)	n (xx.x%)	n (xx.x%)	n (xx.x%)	n (xx.x%)
Follow-up (Day 86 - Day 99)	n (xx.x%)	n (xx.x%)	n (xx.x%)	n (xx.x%)	n (xx.x%)

N= All Subjects enrolled (displayed according to assigned treatment) and denominator for percentage calculations.

[1] If a subject reported more than one abnormal result for a given analyte at any point during the study, only the result with the highest grade is counted.

[2] Indicates the route of administration by which the subject was receiving study drug at the time the laboratory result was recorded.

*Note to programmer: 1) Use TRTA to create the rows within each analyte. 2) For each value of PARAMCD select the highest grade for each subject, regardless of visit or period. 3) Count the frequency by analyte, period, and grade.*  
*Only include analytes with abnormal results in the data in this table.*

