##### **3.2.2. Safety (SAF) Population**

All subjects who receive at least one partial dose of study drug will be included in the SAF Population. Subjects will be analyzed according to the treatment (dose regimen) they actually received. The SAF Population will be used for the safety analyses.

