#### **4.3.3. Clinical Laboratory Parameters**

Summary statistics will be presented for laboratory measurements overall for all subjects in the SAF Population. The following analytes will be tabulated/listed:

- **Hematology:** complete white blood cell count with differential, hemoglobin, hematocrit, and platelets.

- **Serum chemistry profile:** albumin, alkaline phosphatase, alanine aminotransferase (ALT), amylase, aspartate aminotransferase (AST), blood urea nitrogen, calcium, chloride, creatine phosphokinase, creatinine, direct bilirubin, gamma glutamyl transferase, glucose, lactate dehydrogenase magnesium, phosphorus, potassium, sodium, total bilirubin, total protein, and uric acid. In addition, eGFR will be presented using the following formula:  $eGFR = 1.86 \times [Creatinine/88.4]^{-1.154} \times [Age]^{-0.203} \times [0.742 \text{ if female}] \times [1.210 \text{ if Black}]$ .
- **CD4+ Cell Counts**

Urinalysis results will be presented in a data listing and will include results from microscopic testing only. Pregnancy test, Serum Follicle-Stimulating Hormone (FSH) test, Hepatitis Serology, C-reactive Protein, Prothrombin Time and Partial Thromboplastin Time, and Viral Resistance Testing will also be presented in data listings only.

Normal ranges for the laboratory parameters will be provided by the laboratory that performed the assessments. All normal ranges will be standardized and results will be reported in standard units. The tables will include summary statistics for the assessments and the changes from Baseline to each subsequent time point of measurement. A table of subjects with abnormal (i.e., outside normal range) laboratory assessments will also be presented as a frequency of the incidence of each DAIDS toxicity grade (1 – 4) and route of administration.

Potentially Clinically Significant (PCS) criteria may be applied to laboratory parameters as clinically indicated, and if applied, will be summarized as described above. PCS is defined as a laboratory value that is lower or higher than a laboratory's normal range limits.

Note: Electronic clinical laboratory data will be received at Westat. Data reconciliation will be performed to resolve any discrepancies with the Oracle database. Details of data receipt will be described in the Data Receipt Plan.

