**Notes Applicable to All Tables**

General Programming Notes:

1. The tables will be programmed to show aggregate data only.
2. Review the data prior to programming. Check the data for inconsistencies and anomalies. Report suspected data errors to the lead programmer who can determine if they should be addressed by DM.
3. Follow the Quality Control Plans (\\\Westat.com\dfs\CTWRKGRP\PUBLIC\Resources\DA\QC\_Plans) for Tables, Listings, and Graphs. Perform the quality checks, using the Checklist.
4. Always check the population totals. All subjects should be accounted for in all tables. A row for "Unknown" or "Missing" values can be added to any table as appropriate to account for all subjects.
5. For summary statistics: N should always be an integer; minimum and maximum should have the same number of significant digits as is present in the data; mean and median should be calculated to be one additional significant digit than the data collected; standard deviation should be calculated to be two additional significant digits than the data collected.
6. Percentages should be calculated to one decimal place. The true number of treated subjects, which appears at the top of columns in most tables should be calculated once in libnames.sas and put into macro variables to ensure consistency. This number should not be re-calculated when calculating percentages.
7. Follow the mocks, especially regarding details, such as titles, capitalization, order of columns and row labels, and footnotes. Standard table formatting may be followed, as some mocks may have been created due to space/pagination considerations. The visit names in the mocks are examples only. Consult the protocol and SAP and present all scheduled visits for the item in question.
8. Additional footnotes may be required to fully/more accurately describe the contents of a table (decided during development). Consult project leader and lead biostatistician with questions.

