**Table 14.3.2.2**  
**Abnormal Laboratory Results by DAIDS Toxicity Grade [1] and Route of Administration**  
**Safety Population - IM HIV Uninfected Group**

Test/Route of Administration [2]	IM HIV Uninfected (N=XX)				
	Grade 0 n (%)	Grade 1 n (%)	Grade 2 n (%)	Grade 3 n (%)	Grade 4 n (%)
Analyte 1					
IV Infusion (Day 1 - Day 29)	n (xx.x%)	n (xx.x%)	n (xx.x%)	n (xx.x%)	n (xx.x%)
IM Injection (Day 30 - Day 85)	n (xx.x%)	n (xx.x%)	n (xx.x%)	n (xx.x%)	n (xx.x%)
Follow-up (Day 86 - Day 99)	n (xx.x%)	n (xx.x%)	n (xx.x%)	n (xx.x%)	n (xx.x%)
Analyte 2					
IV Infusion (Day 1 - Day 29)	n (xx.x%)	n (xx.x%)	n (xx.x%)	n (xx.x%)	n (xx.x%)
IM Injection (Day 30 - Day 85)	n (xx.x%)	n (xx.x%)	n (xx.x%)	n (xx.x%)	n (xx.x%)
Follow-up (Day 86 - Day 99)	n (xx.x%)	n (xx.x%)	n (xx.x%)	n (xx.x%)	n (xx.x%)

N= All Subjects enrolled (displayed according to assigned treatment) and denominator for percentage calculations.

[1] If a subject reported more than one abnormal result for a given analyte at any point during the study, only the result with the highest grade is counted.

[2] Indicates the route of administration by which the subject was receiving study drug at the time the laboratory result was recorded. The pre-steady state period is not included.

*Note to programmer: 1) Use TRTA to create the rows within each analyte. 2) For each value of PARAMCD select the highest grade for each subject, regardless of visit or period. 3) Count the frequency by analyte, period, and grade.*  
*Only include analytes with abnormal results in the data in this table.*

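### The IM SAP's laboratory-grade tables by route keep one worst grade per subject for the whole study, so a route row can understate that route's abnormalities

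*SAP*

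**What the plan says.** IM SAP 4.3.3 describes a table of subjects with out-of-range laboratory results that "will also be presented as a frequency of the incidence of each DAIDS toxicity grade", from 1 to 4, and by route of administration.

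The mock tables carry this out as Table 14.3.2.1 (HIV infected) and Table 14.3.2.2 (HIV uninfected). Each has three rows per analyte: IV infusion (Days 1 to 29), IM injection (Days 30 to 85) and follow-up (Days 86 to 99). The columns are Grades 0 to 4.

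- The note to programmer, identical in both tables, builds the rows from TRTA. It then says to "select the highest grade for each subject, regardless of visit or period. 3) Count the frequency by analyte, period, and grade".
- Footnote [1] states the same rule: if a subject has several abnormal results "for a given analyte at any point during the study, only the result with the highest grade is counted".
- Footnote [2] places the result in the route being received when it was recorded. In Table 14.3.2.2 it adds: "The pre-steady state period is not included".
- The N line under both tables reads "N= All Subjects enrolled (displayed according to assigned treatment) and denominator for percentage calculations", although both titles say Safety Population.

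IM SAP 3.2.2 says of the Safety Population: "Subjects will be analyzed according to the treatment (dose regimen) they actually received".

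**The concern.** Rows labelled by route invite the reader to compare IVI with IM. That needs each subject's worst grade within each route. Here the maximum is taken over both routes before the rows are formed, so each subject and analyte contributes one result. When the two routes differ in grade, the lower one vanishes, even if it was abnormal. Two further cases are left open: equal worst grades on both routes, and the order of excluding the pre-steady-state phase and selecting the maximum.

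What is at stake is a safety display. IM safety is a primary objective (IM SAP 2.2.1), and no other planned output summarises laboratory DAIDS grade by route. The by-period AE severity tables (14.3.1.3.2 and 14.3.1.3.3) include a laboratory change only if it was judged clinically significant (Protocol 8.3). The laboratory listings print results, period and normal limits but have no grade column.

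**Working it through.** The plan gives no figure that depends on this rule, so there is nothing to reproduce. The check applies two counting rules to the same data: the highest grade within each route, and the mock-table rule.

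**Direction.** A subject counted in a route row at grade g has study-wide maximum g, reached on that route, so the within-route maximum is also g. No cell can be too high. Of the 16 pairs of abnormal grades (1 to 4 on each route), 6 lose the IM abnormality, 6 lose the IVI abnormality and 4 are ties.

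**Constructed example** (assumed data, group of 10; IM SAP 3.1 gives 20 in total over both tables, and the split by HIV status is not stated):

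- 2 subjects Grade 2 on IVI and Grade 1 on IM
- 1 abnormal on IVI only
- 1 abnormal on IM only
- 6 with no graded abnormality

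Within route: IVI 2 + 1 = 3/10 and IM 2 + 1 = 3/10. Mock rule: IVI 2 + 1 = 3/10 and IM 1/10. No abnormal grades are tied, so the result is the same under any tie rule. Swapping the route labels gives 1/10 and 3/10, so the rule does not inherently favour IM.

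**Expected size** (assumed rates, no route effect). Sampling every 2 weeks (Protocol 6.3) puts Days 1, 15 and 29 in the IVI row and Days 43, 57, 71 and 85 in the IM row: 3 and 4 draws by row label. Assume that abnormal results split 60/25/10/5% over Grades 1 to 4. With per-draw abnormality rate p and k independent draws, P(max ≤ g) = (1 − p × share above g)^k.

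At p = 10%, P(max ≤ g) for g = 0, 1, 2, 3 is:

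- IVI (k = 3): 0.7290, 0.8847, 0.9557, 0.9851
- IM (k = 4): 0.6561, 0.8493, 0.9413, 0.9801

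The true percentage abnormal is 1 − 0.7290 = 27.1% on IVI and 1 − 0.6561 = 34.4% on IM. The IM abnormality is lost under every tie rule when the IVI grade is higher: 0.1932 × 0.1153 + 0.0920 × 0.0443 + 0.0388 × 0.0149 = 0.027. The same sum for IVI is 0.1557 × 0.1507 + 0.0710 × 0.0587 + 0.0294 × 0.0199 = 0.028.

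Percentage points lost under every tie rule, IVI / IM. Persistent means a normal subject effect with SD 2 on the logit scale, with the marginal rate held at p:

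| p per draw | independent | persistent |
|---|---|---|
| 5% | 0.8 / 0.8 | 2.0 / 1.7 |
| 10% | 2.8 / 2.7 | 4.6 / 3.8 |
| 20% | 9.3 / 8.5 | 10.2 / 8.2 |

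Multiplying by 10 subjects gives about 0.1 to 0.2 subject per analyte at 5% and 0.8 to 1.0 at 20%. The grade split matters: at 20%, independent draws, the loss is 6.0 / 5.4 points with an 80/15/4/1 split and 3.4 / 3.1 with 90/8/1.5/0.5, which is 0.3 to 0.6 subject.

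**Tie rule.** At 10%, independent, 60/25/10/5, the true IM minus IVI difference is 34.4 − 27.1 = +7.3 points. The table shows 27.9 − 24.3 = +3.6 if ties go to IVI, 31.7 − 20.5 = +11.2 if they go to IM, and 31.7 − 24.3 = +7.4 if they appear in both rows.

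**Pre-steady state.** Protocol Table 2 schedules haematology and chemistry at each of the four pre-steady-state dosing visits. If the maximum is taken first, regardless of period, and falls in that phase, the exclusion in footnote [2] leaves the subject in no row.

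**The case against.** IM SAP 4.3.3 does not say that the highest grade is taken within each route. Classifying each subject's single worst result by grade and route also fits its words, and footnotes [1] and [2] disclose that rule. This is fair as to wording. It does not rescue the display, because every subject receives both routes in sequence and the rows exist to compare them.

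Other outputs soften the effect. The by-period haematology and chemistry tables give range and change from baseline, Listing 16.2.8.5 shows every abnormal result with its period, and Protocol 7.2.1 has Grade 3 and 4 results repeated and discussed. None of these gives graded counts by route.

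The size calculation rests on assumed rates and splits. It has two rows and omits the uninfected subjects' Day 99 draw, which could take the maximum in Table 14.3.2.2. These limits stand.

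A reader might also infer three stronger points that the documents do not support:

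- **The rows ignore treatment received.** TRTA and footnote [2] already follow the treatment received, and general note 6 of the mock tables describes the column N as treated subjects. The N line looks carried over and matters only if an enrolled subject was never dosed.
- **The infected Follow-up row has no scheduled data and should go.** Laboratory sampling does end at Day 85, but that visit has a ±1 day window and IM SAP 3.4.1 assigns period by visit date. A Day 85 sample drawn on Day 86 would fall in that row.
- **Grade 0 cells lose normal subjects.** Grade 0 is not defined. In a table of abnormal results it could mean out of range but ungraded.

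**Conclusion.** The point holds for the selection rule, the missing tie rule and the unstated order of the pre-steady-state exclusion. The rows can only understate route-specific incidence. That they would systematically favour IM, or reverse the comparison, does not follow: the direction depends on the data and the tie rule. A reversal appears only under particular assumptions, for example 20% per draw, persistent, ties to IVI, where true values of 37.4% (IVI) and 42.6% (IM) print as 27.2% and 25.5%.

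The loss is small for rare abnormalities and up to about one subject per analyte for common ones, given a table of 10 and the assumed rates and grade splits. The tables are descriptive and no decision rule uses them. The point is minor to moderate: worth correcting before programming, with no bearing on the PK bridge.

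**What to change.** In both tables:

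- Note step 2: for each PARAMCD, select the highest grade for each subject within each route period; a subject may be counted in more than one row. This also settles ties.
- Footnote [1]: where a subject has more than one result for an analyte within a route period, only the highest grade in that period is counted.
- N line: Safety Population subjects with at least one result for the analyte in that period. This follows the non-missing rule in IM SAP 3.4.1 but needs a stated exception to general note 6, which says of the column total: "This number should not be re-calculated when calculating percentages".
- Define Grade 0. If it covers every result that is not Grade 1 to 4, the grades in each row add up to its denominator, which serves general note 4: "All subjects should be accounted for in all tables".
- Print the number of scheduled draws per period. State whether the pre-dose Day 1 sample belongs to the IVI row, as the row label implies, or to the period before it, as the laboratory listing footnotes imply (3 v 4 or 2 v 4 draws). The SAP's period figure may settle this but is not visible in the public copy.

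In Table 14.3.2.2, remove pre-steady-state results before selecting the highest grade. In Table 14.3.2.1, keep the Follow-up row, but assign the scheduled Day 85 pre-dose sample to the IM period by nominal visit even if drawn on Day 86.

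The cost is a few lines in two mock tables and a by-period step in one program. Subjects may then appear in several rows, and the unequal number of draws remains, but both are shown.
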